### Sample Size for Testing the primary hypothesis in this study.

We have estimated the sample size of the prospective cohort based on the primary hypothesis that individuals experiencing the intervention of Phase III will have higher levels of effective use of SARS-CoV-2 testing than their testing at baseline. The McNemar test, together with the odds ratio (OR) of COVID-19 testing for post-intervention versus baseline, will be used to assess the intervention effect. Preliminary data yielded a discordance of 19% between baseline and follow-up measurements. The ORs were 3.4, 2.3, and 2.3 for Harris, Cameron, and NETX, respectively. The OR for the pooled data was 2.55. We use an OR of 2.5 and a discordance of 19%, which represents an 8% difference in the proportion of testing at follow-up compared to baseline, to size the prospective cohort. For a one-sided test at the significance level of 2.5%, a **sample size of 237 is needed to provide 80% power** for confirming the intervention effect. To allow for a **45% loss to follow-up**, 431 participants need to be enrolled at baseline. The table below provides the size options for a one-sided McNemar test of alpha 2.5% and power 80%.

Proportion of discordance	Odds ratio (OR)	Difference in proportion of testing pertaining to OR	Required sample size	Enrollment allows for a 35% loss to follow-up	Enrollment allows for a 45% loss to follow-up
0.19	2	6%	393	605	715
0.19	2.5	8%	237	365	431
0.19	3	9.5%	177	273	322
0.3	1.5	6%	681	1048	1239
0.3	1.727	8%	387	596	704
0.3	2	10%	249	384	453
0.3	2.75	14%	128	197	233

**Statistical Analysis - MC-NET-JITAI.** We will analyze the secondary outcome measures using the McNemar test, conditional logistic regression model, generalized linear mixed model (GLMM). The enrolled individuals completing the follow-up survey constitute the analysis set. In GLMM, we will specify proper random effects to account for hierarchical nesting structure. Secondary analyses will examine the relation between knowledge, attitudes, and intentions on testing and vaccination decisions and we will use the same multilevel GLMM models.

**Resource Sharing.** All unique research resources developed as part of the proposed collaboration between UTHealth, the University of Texas Health Science Center at Tyler (UTHSC-T), and other project partners will be made available to the public upon request at the end of the grant period. Examples include dissemination models, recruitment, and data collection protocols, as well as study instruments. All requests for research resources should be sent electronically to the primary PI.

**Data Sharing.** We recognize that the funder requires the RADx-UP testing intervention projects to use rapid scale-up of rigorous research strategies and integrate data collected across the sites to maximize improvements in public health control of the pandemic. Thus, to the extent possible, data acquisition, collection, and curation strategies will be coordinated with the CDCC guidance for annotation and benchmarking of data, including obtaining appropriate consent for data sharing. A data-sharing plan will apply to qualitative, quantitative, and process data collected during the research studies. Project study staff will make RADx-UP intervention data available after the primary finding's manuscript is accepted for publication or 18 months after Phase III study completion, whichever occurs first. The guidelines for data sharing and the use of multisite data in our region will be used for sharing data by the participating site in our proposal. The complete study data files, with sufficient data documentation for proper analysis, will be made available to the public on a secure website requiring password identification for access. The

final datasets will be stripped of all personal identifiers prior to release for sharing, but to ensure confidentiality of all participants, and that the data are used only for research, we will also require a data sharing agreement that provides for: (1) a commitment to using the data only for research purposes and not to identify any individual participant; (2) a commitment to using best statistical and ethical practices in analyzing and reporting finding; (3) a commitment to securing the data using appropriate information technology; (4) a commitment to crediting the source and the funding agencies of the original project in all publications and presentations; and (5) a commitment to destroying or returning the data after analyses are completed.

**Publication Plan:** The following guidelines have been established by our project, through a publication committee, for requesting data and for the utilization of data.

General Guidelines:

- 1) Data requested must be for the purpose of performing research and publishing the results. Any extrinsic use of this multisite data must be approved by our publication committee, including abstracts, manuscripts, public presentations, and preliminary data in grant applications.
- 2) The Publication Committee will review all proposals to ensure absence of conflict with previously approved proposals, determine merit, and record the date and the approval of proposals. Members of the publication committee will also have the opportunity to voluntarily assist with the proposed research and form a writing group.
- 3) The electronic dataset files will be stored in a confidential manner on a password-protected computer in a locked office or in a locked file cabinet in a locked office so as to protect the confidentiality of subject information, if applicable. Multisite data will not be released to individual PIs without written consent of all other site PIs who contributed data to the multisite data.
- 4) Errors and uncertainty are inherent in all data and any errors may affect the final results and research findings. For this reason, any data discrepancies or anomalies identified during data management and analysis can address these issues, maintain the quality of all data.

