**NCT 07074171**

**Version Date: 11/07/2024**

**Protocol Template Version July 2024**  
*Adapted from NIH protocol template and ICH Guidelines*

Protocol Title:	Influencing Factors of COVID-19 Testing: Main Study 2024
Principal Investigator:	[name], UTHealth School of Public Health in Houston
Co-Investigators:	[name], UTHealth School of Public Health in Brownsville and Rio Grande Valley; [name], UT Health Science Center at Tyler; [name] UTHealth School of Public Health in Houston, [name], UTHealth School of Public Health in Houston, [name] [name], UTHealth School of Public Health in Houston,
Study Coordinator:	[name], [name], [name]
Population:	431 individuals in the intervention group, Male, Female, 18-89, general population sample drawn from the community through door-to-door outreach and community events in Northeast Texas, Harris County, and South Texas.
Number of Sites:	Three sites: Houston, Lower Rio Grande Valley, and Tyler, UT Houston is the lead site of the multi-site study
Study Duration:	The study will run from July 2024 - February 2025
Subject Duration:	Intervention study participants will be enrolled, complete a baseline survey, and participate in a text message-based educational intervention throughout the study. They will be followed up by phone or in person for 8 weeks. For the control group participants' information, we will use a historical control group (the Control group from the phase II Embedded Study trial that completed a baseline and follow-up survey).

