## Objectives

The primary objective of this study is to:

- 1) Determine the effectiveness of the adapted MC-NET-JITAI (Multilevel Community network-informed Just-In-Time-Adaptive Intervention) versus a historical control group.

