### Control Arm:

**Control PBGs:** Since we are utilizing a historical control study design, we are not recruiting any new control participants for this Phase III main study. Instead, we will analyze the survey data already collected from the Phase II embedded study control participants.

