## Statistics

**Statistical Analysis - Main Study Primary Outcomes.** We will conduct a series of analyses regarding the primary outcome variable - testing for COVID-19. First, we will conduct McNemar's test on data from the prospective cohort only. In addition to the test p-value, the odds ratio of COVID-19 testing for post-intervention versus baseline will be evaluated to assess the intervention effect. Second, based on both the prospective cohort and historical controls, we will find inferences for the ratio of odds ratios for intervention versus control. Third, using the prospective cohort, we will build a multi-level generalized linear mixed model (GLMM) including time as a fixed effect factor to evaluate intervention effect. Multiple random effects will be specified to account for the hierarchical structure of persons nested within PBGs nested within regions. Additionally, we will test variables such as individual demographics and baseline measures of rapid testing uses and include significant variables as the fixed effect factors. We will also test the PBG-level of Social Determinants of Health (SDOH) (e.g., % of minority, % of people with no insurance) to investigate the SDOHs as a potential effect modifier on the intervention effectiveness. We will also compute various network measures based on personal networks and organization affiliation patterns associated with COVID-19-related outcomes. Finally, we will build a GLMM to data of both the prospective cohort and historical controls. We will specify proper random effects to account for hierarchical nesting structure.

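### The only primary objective is a comparison with historical controls, but the primary hypothesis, the McNemar test and the 80% power concern pre-post change in the intervention cohort alone

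*Combined protocol and SAP*

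**What the plan says.** The Objectives section has a single entry: "Determine the effectiveness of the adapted MC-NET-JITAI (Multilevel Community network-informed Just-In-Time-Adaptive Intervention) versus a historical control group".

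The sample-size section works from a different statement. Its primary hypothesis is that people receiving the Phase III intervention will have "higher levels of effective use of SARS-CoV-2 testing than their testing at baseline". It says that the McNemar test, with the post-versus-baseline odds ratio, "will be used to assess the intervention effect". At a one-sided 2.5% level, a "sample size of 237 is needed to provide 80% power", and the text describes that power as being for confirming the intervention effect. Every row of the table is for the same one-arm test.

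The Statistics section announces a series of analyses of the primary outcome. McNemar on the prospective cohort comes first. Second, "we will find inferences for the ratio of odds ratios for intervention versus control". Third is a GLMM on the cohort alone. Last, "we will build a GLMM to data of both the prospective cohort and historical controls". None is named as primary.

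On the controls, the Control Arm section says "we will analyze the survey data already collected from the Phase II embedded study control participants". The Study Design section puts their number at 400. The summary table gives the Phase III calendar: "The study will run from July 2024 - February 2025".

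**The concern.** The objective asks whether the intervention does better than no intervention. The McNemar test asks whether the same people test more at follow-up than at baseline. A rise from any cause, such as season, test availability or a COVID-19 wave, counts as success in the second question but not in the first.

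Two consequences follow. If McNemar is significant and the controlled analyses are not, the plan does not say whether the objective was met, and the sample-size wording would support saying that it was. The trial's chance of meeting its actual objective is also unstated, and a reader may take 80% for it.

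The controlled analyses have a limit of their own. The control data were collected in Phase II, so they can remove a trend that was present then but not one specific to July 2024 to February 2025. The plan draws no such limitation.

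**Working it through.** **1. Reproduce the plan's figure.** Inputs from the sample-size section: n = 237, discordance 0.19, odds ratio (OR) 2.5, one-sided 2.5%, 45% loss.
- The share of discordant pairs favouring follow-up is 2.5/3.5 = 0.714. The exact one-sided McNemar test, averaged over the binomial number of discordant pairs, has power 0.800.
- 237/(1 − 0.45) = 430.9, so 431.

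Both figures are right for the one-arm test. No control quantity enters.

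**2. Power of the controlled comparison.** The documents give 400 controls with both surveys, but no control discordance or control pre-post OR. Both are assumed below.

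Test of the ratio of ORs, one-sided 2.5%:
- Expected discordant pairs, intervention: 237 × 0.19 × 2.5/3.5 = 32.2 and 237 × 0.19 × 1/3.5 = 12.9.
- Expected discordant pairs, controls with OR 1.0 and discordance 0.19: 400 × 0.19/2 = 38 each way.
- SE = √(1/32.2 + 1/12.9 + 1/38 + 1/38) = 0.402.
- Power = Φ(ln(2.5/1.0)/0.402 − 1.96) = Φ(0.32) = 0.626.

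The same formula at other control ORs, with discordance held at 0.19:

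| Assumed control OR | Power (formula) | Power (simulation, 400,000 runs) |
|---|---|---|
| 0.8 | 0.808 | 0.829 |
| 0.9 | 0.720 | 0.737 |
| 1.0 | 0.626 | 0.638 |
| 1.2 | 0.446 | 0.445 |
| 1.5 | 0.243 | 0.234 |

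**3. Sensitivity at control OR 1.0.**
- Control discordance of 10% or 30% gives 0.518 or 0.681 on the ratio-of-ORs scale.
- On the difference-in-proportions scale, the intervention change is 0.19 × 1.5/3.5 = 0.0814. The squared SE is (0.19 − 0.0814²)/237 + d/400, where d is control discordance. Power is 0.721, 0.635 and 0.550 for d = 10%, 19% and 30%. The direction is opposite to that on the OR scale, so power must be quoted on the scale of the chosen analysis.
- The figures above ignore clustering within priority block groups (PBGs). An assumed design effect of 1.2 or 1.5 on the whole variance lowers 0.626 to 0.548 or 0.461.

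**4. What each test does when the intervention has no effect.** Assume a secular pre-post OR of 1.5 or 2.0 during Phase III (no document source), with n = 237 and discordance 0.19.

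| Test | Rejects at secular OR 1.5 | Rejects at secular OR 2.0 |
|---|---|---|
| One-arm exact McNemar | 22% | 56% |
| Ratio of ORs, trend absent from Phase II controls | 19% | 43% |
| Ratio of ORs, same trend in Phase II controls (simulation) | 2.3% | 2.3% |

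The controlled test holds its level only when the controls carry the same trend.

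**The case against.** The plan does not claim that the 80% covers the controlled comparison. It says that the prospective cohort was sized against its own baseline, and it labels the table as a McNemar table. The two controlled analyses sit under the primary-outcome heading, so treating McNemar as decisive would mean disregarding analyses that the plan commits to. The controls are openly called historical throughout, and the Study Design section says PBGs will be matched on size, testing and vaccination rates and a disparities index. The power figures rest on assumed control values and run from 24% to 81% on the control OR alone. They also take the planned 45% loss as given: at the table's 35% option, 431 enrolled would leave 280 completers and the 63% becomes 67%.

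Much of this is fair. The documents cannot show that controlled power is below 80%, only that it is unstated and could be well below. PBG matching helps comparability but does not remove calendar time. The eligibility criteria are stated for the intervention arm and exclude anyone tested in the past 30 days. The documents do not say whether controls were screened alike or what recall window the outcome uses. A ratio of ORs could carry a bias from that, and naming it as primary would not cure it.

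What the objection leaves in place is the mismatch. The only stated primary hypothesis is uncontrolled, the only stated objective is controlled, and no analysis is tied to the objective.

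**Conclusion.** The concern holds and should be fixed before results are seen. That the 80% does not apply to the stated objective follows from the text alone and needs no assumption. The sizing arithmetic is not in error; it answers a different question. The size of the gap is illustrative: about 63% power if controls show no net change with 19% discordance, before clustering. A fall in control testing would raise it, and any rise or a design effect above 1 would lower it. The plan as written would let an uncontrolled pre-post result stand as proof of effectiveness against controls.

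**What to change.** - Name one controlled analysis already in the Statistics section as the single primary analysis for the objective: either the ratio of ORs, or the group-by-time effect in the combined GLMM with PBG random effects. Make the choice before looking at the observed change in the controls.
- Label the McNemar test and the cohort-only GLMM supportive, and say that neither can establish effectiveness by itself.
- State that the 80% applies only to the one-arm test.
- Report power for 237 completers against 400 controls on the scale of the chosen analysis. Use the Phase II control discordance and change, which are already held, or give a range with its assumptions.
- State that the controls are not concurrent, so the comparison removes the Phase II trend but not secular or seasonal change specific to Phase III.

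The cost is protocol and SAP wording plus one power calculation. The stated power may become less favourable. Enrolment stays at 431 and no data are added.

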In Phase III, we will build off of the Phase II embedded study with some adjustments to the design to address new research priorities that examine an intervention that is network informed and delivered through community health worker interactions plus digitally-delivered intervention content with the goal of increasing COVID-19 testing and vaccination. This model, if proven effective, can be scaled up to address COVID-19 and other future pandemics. We will utilize the sample of intervention PBGs used in Phase II and will recruit and enroll participants not previously enrolled in either phase I or II from these PBGs using convenience sampling methods. We will use a historical control group consisting of participants from our control arm in Phase II who completed both their baseline and follow-up surveys embedded in the study.

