## Summary of Embedded Study Survey Constructs

Measures / Constructs	Questions	Citation/Tool
Testing behavior	Testing for COVID-19, ever tested, last 30 days, positivity, access to testing	Funder required items, Novel items
COVID-19 history	COVID-19 sickness, hospitalization (self or others)	Funder required items, Novel items
Intention to test	Likelihood of testing (ever, 30 days), intention to test as needed	Funder required items, Novel items
Self-efficacy to test	Certainty of ability to be tested given situational contexts	Adapted self-efficacy measures following Maibach (1995) 
Pandemic safety behaviors	Wearing masks in private settings, wearing masks in public settings, washing/sanitizing hands, intentional social distancing (Never, some of the time, very often, all of the time)	Adapted for CEAL Program from Center for Economic and Social Research Understanding America Study Coronavirus Tracking Survey. https://www.phenxtoolkit.org/covid19/source
Vaccination	Vaccine uptake, type, doses	Funder required items
Trusted Sources of Information	Sources of information (doctor, media, health department, etc)	Funder required items
COVID-19 Perceived Susceptibility/Severity	How concerned are you about contracting COVID-19? How likely is it that you will get COVID-19?	Savoia E. et al, 2021 

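### No comparison with the historical controls is prespecified for vaccination, so a pre-post change cannot be told apart from background uptake

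*Combined protocol and SAP*

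**What the plan says.** The Objectives section sets one aim: effectiveness of the intervention "versus a historical control group". The General Information section describes the Phase III intervention as delivered "with the goal of increasing COVID-19 testing and vaccination". Vaccination uptake is a listed secondary outcome, with no time window or scoring rule.

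For testing, the Statistics section separates cohort-only from controlled analyses. It begins: "First, we will conduct McNemar's test on data from the prospective cohort only". It then brings in the controls: "based on both the prospective cohort and historical controls, we will find inferences for the ratio of odds ratios for intervention versus control". It ends with a GLMM fitted to both groups. The whole series is introduced as concerning the primary outcome, testing.

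For the secondary outcomes, the paragraph on statistical analysis of MC-NET-JITAI, at the end of the sample size section, says: "We will analyze the secondary outcome measures using the McNemar test, conditional logistic regression model, generalized linear mixed model (GLMM"). It continues: "The enrolled individuals completing the follow-up survey constitute the analysis set". On the model it adds only: "In GLMM, we will specify proper random effects to account for hierarchical nesting structure". It mentions no controls, group term or group-by-time term.

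The table of embedded-study survey constructs lists "Vaccine uptake, type, doses", and the Study Design section says that the 400 controls completed both the baseline and the follow-up survey.

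**The concern.** Some participants will be vaccinated between the two surveys whatever the study does. The follow-up visit may fall anywhere from 5 weeks to about 4 months after the first visit (Recruitment section), in a study that runs from July 2024 to February 2025. A paired pre-post test counts every such vaccination as evidence of change.

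For testing, the plan supplies a second group against which to judge that change. For vaccination it does not say that it will. Raising vaccination is half of the stated goal, and the objective names a comparator. A result from the pre-post methods alone could not answer that objective for vaccination, and a small background uptake could make it statistically significant.

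**Working it through.** **Inputs from the documents.** 237 completers, 431 enrolled, one-sided 2.5% level, discordance 0.19, odds ratio 2.5, 45% loss to follow-up (sample size section); 400 controls (Study Design).

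**Assumptions.** Vaccination is scored as cumulative status; the intervention has no effect; background uptake between surveys is u. The documents give neither the scoring nor u, so u is varied.

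**1. The plan's own figure.** The difference in proportions is 0.19 × (2.5 − 1)/(2.5 + 1) = 0.0814, stated as 8%. Exact one-sided McNemar power, summed over the number of discordant pairs, is 0.8001 at N = 237. Enrolment is 237/(1 − 0.45) = 430.9, so 431. Both figures reproduce. They concern testing; no sample size is given for vaccination.

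**2. Threshold for vaccination.** If status can only rise, all discordant pairs go one way and the exact one-sided p for k new vaccinations is 0.5^k.
- k = 5: 0.031, not significant at 2.5%.
- k = 6: 0.0156, significant. Six of 237 is 2.5%.

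A two-sided test at the general 0.05 level has the same threshold: 2 × 0.0156 = 0.031, against 2 × 0.031 = 0.0625 for k = 5.

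**3. False-positive probability of the pre-post test.** P(X ≥ 6) with X ~ Binomial(237, u):

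| Background uptake u (assumed) | P(significant), no intervention effect |
|---|---|
| 0.5% | 0.1% |
| 1% | 3.3% |
| 2% | 33.8% |
| 3% | 71.7% |
| 5% | 98.0% |

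**4. Other scoring.** If status could move both ways, with discordance borrowed from the testing outcome (0.19, an assumption), a background shift of 3 points is significant 15% of the time, 5 points 37% and 8 points 78%. The inflation is smaller but remains.

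**5. Comparison with the controls.** Let a and b be the numbers with a new dose among 237 and 400, and p̄ = (a + b)/637. The statistic is z = (a/237 − b/400)/√[p̄(1 − p̄)(1/237 + 1/400)], with rejection above 1.96. Summing the two binomial distributions, with no intervention effect:

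| Background uptake, cohort versus controls (assumed) | P(significant) |
|---|---|
| Equal, 2% to 10% | about 2.6% |
| 3% versus 2% | 13% |
| 5% versus 3% | 25% |
| 5% versus 2% | 54% |

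At a cohort uptake of 5%, the cohort-only test rejects 98% of the time. The controlled test rejects 54% even when the controls' background uptake was only 2%. Its power is about 80% for 8% versus 3% or 11% versus 5%, ignoring clustering within census block groups.

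**The case against.** The strongest reply is that the plan is silent on this and does not exclude the controls. A GLMM is not inherently pre-post: the Statistics section fits one to the cohort and another to both groups, and the secondary paragraph's sentence on random effects closely matches the one that follows the combined model. Conditional logistic regression can carry a group-by-time term. The analysis-set sentence also appears under Missing data, where it coexists with two controlled primary analyses, so it cannot by itself shut the controls out. The Objectives and Control Arm sections are not limited to testing. All of this stands. A reader might infer that vaccination will be analysed only within the cohort, or that background uptake will be reported as an effect; the documents state neither.

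The reply does not dispose of the point. A comparison that has to be inferred is not prespecified, and the Statistics section shows that the authors name the controls when they mean to use them. McNemar's test, which is named, cannot separate background uptake from effect.

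Two further objections limit the size. The probabilities depend on assumed scoring and assumed rates, and at 1% uptake or below the problem is negligible. The controls are also an imperfect remedy, because they come from an earlier phase. If background uptake was higher then, the comparison would be biased against the intervention instead.

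**Conclusion.** The concern holds for vaccination, as a gap in prespecification combined with a named test that gives a biased answer if used to claim effectiveness. Under cumulative scoring and no intervention effect, the false-positive probability is near nominal at 1% background uptake (3%), about a third at 2%, and 72% to 98% at 3% to 5%. These rates are assumptions. That usable vaccination data exist for the controls is inferred from the construct table and their completed surveys; the plan does not say so directly.

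A reader might extend the argument to all secondary outcomes. The documents do not support that: mitigation is defined only after a positive test, so its pre-post analysis raises a different problem that a control comparison of this kind does not address. Nor should the controlled comparison be taken as a full cure, since it holds its error rate only if background uptake was the same in both periods.

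**What to change.** In the paragraph on statistical analysis of MC-NET-JITAI:

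- Define the vaccination outcome as receipt of a new COVID-19 vaccine dose between baseline and follow-up.
- Compare it between the intervention cohort and the historical controls with the same two-group GLMM planned for testing, and state that the controls are part of this analysis set.
- Label the cohort-only pre-post vaccination result as descriptive, with no claim of effectiveness.
- State that the controls come from the earlier Phase II, so that the comparison reduces calendar-period bias but does not remove it. The documents do not currently contain such a statement.
- If the control vaccination data prove unusable, keep the descriptive label alone.

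The cost is a change of wording and one more model on data that appear to be already collected. The controlled estimate will be less precise than the pre-post one. At 80% power and before any allowance for clustering, the detectable difference is about 5.2 points over a 3% control rate, 6.2 over 5% and 7.9 over 10%.
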